8.1.3.5. Group 1B: Days 31 to 36 (At home)

On Days 31 to 37, the participant is to self-administer ciprofloxacin 500 mg po every 12 hours at home [at about the same times (\pm 30 min) each day]. The participant will continue with the e-diary as described in [Section 8.3.5.1](#). The site must contact the participant to remind them to start their third course of ciprofloxacin within 24 hours of Day 31.

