IP Group	Treatment Group	Treatment	Sample Size (N)	
1 Cipro	1A	AV7909 + ciprofloxacin (with PK assessment)	≈40	≈70
	1B	AV7909 + ciprofloxacin (without PK assessment)	30	
2 Doxy	2A	AV7909 + doxycycline (with PK assessment)	≈40	≈70
	2B	AV7909 + doxycycline (without PK assessment)	30	
3 AV7909	3	AV7909 only	70	
		TOTAL	≈210	

Approximately the first 40 participants who are randomized for either IP Groups 1 and 2, ie, the first 80 participants randomized across all sites to either antibiotic group, will be assigned to Treatment Groups 1A or 2A while those randomized into IP Groups 1 and 2 thereafter will be assigned to Treatment Groups 1B or 2B. Randomization will be stratified by site. A representative racial distribution will be sought among recruited participants and sites will be asked to recruit populations that are gender- and age-balanced (ie, between 40-60% male with 40-60% of participants in the two age ranges of 18 to 30 years of age and 31 to 45 years of age).

[Figure 1](#) displays the overall design used for this study.

Ciprofloxacin (500 mg by mouth [per os] every 12 hours [po q 12 hr]) will be administered to Group 1 on Days 4-9, Days 22-24 and Days 31-37, and doxycycline (100 mg by mouth [per os] every 12 hours [po q 12 hr]) will be administered to Group 2 on Days 2-9, Days 22-24, and Days 32-38. Antibiotics will be administered in three courses that will be used both by site staff for in-clinic visits and by participants when they are at home. The exact format of the courses in terms of number of tablets and when participants will receive each course will be described in the Pharmacy Manual.

The 40 participants in Group 1A will self-administer approximately half (14/31) of the ciprofloxacin doses; the remainder will be administered by site staff during clinic visits. The 30 participants in Group 1B, with far fewer clinic visits than Group 1A due to the lack of PK sampling, will self-administer more than 90% (29/31) of ciprofloxacin doses.

AV7909 Anthrax Vaccine

IND 014451

Protocol EBS.AVA.210, Version 3.0 (28 October 2019)

For the doxycycline groups, the distributions of self-administered doses are similar to those planned for the two ciprofloxacin groups with Group 2A self-administering 15/35 doses and Group 2B self-administering 33/35 doses.

An event schematic for this study is provided in [Figure 2](#).

Ciprofloxacin PK sessions in Group 1A will be conducted on Days 4, 8, 31 and 35.

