4.3.2. Ciprofloxacin

The ciprofloxacin dose (500 mg), dosing schedule [twice a day (q 12 hr)] and route of administration [by mouth (po)] being used in this study are those that would be used for PEP in the event of anthrax exposure and similar to those that were used in the prior PEP study conducted with ciprofloxacin and BioThrax {[EPDG, 2014](#)}. In this study and the prior BioThrax study (Study EBS.AVA.009), ciprofloxacin administration occurs on an intermittent daily rather than a continuous daily dosing schedule, with the assumption that intermittent dosing would achieve the required single dose and steady state concentrations needed prior to and following the vaccination schedule, as well as the immunogenicity endpoints while restricting the antibiotics administered to the minimum to achieve these ends.

Ciprofloxacin will be administered intermittently in three courses that will be used both by site staff for in-clinic visits and by participants when they are at home. The course format in terms of number of tablets and when participants will receive each course will be described in the Pharmacy Manual.

In addition to ensuring the achievement of steady state concentrations before and after the complete two-dose series of the vaccine, the selected ciprofloxacin dosing periods reflect the time when the inflammatory and immunosuppressive effects of ciprofloxacin are most likely to affect the antibody response to AV7909 {[Takahashi et al, 2005](#); [Kaminski et al, 2010](#)}. The

AV7909 Anthrax Vaccine

IND 014451

Protocol EBS.AVA.210, Version 3.0 (28 October 2019)

intermittent dosing schedule was chosen in the hopes of minimizing any adverse effects from ciprofloxacin. This strategy appeared to have been successful in the BioThrax plus ciprofloxacin study in that ciprofloxacin-related AEs were low in number, frequently reported as related to both ciprofloxacin and BioThrax, generally mild in severity and resolved without sequelae by the end of the study {EPDG, 2014}.

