6.1.5. Administration of Ciprofloxacin

Ciprofloxacin (500 mg po q 12 hr) will be administered only to participants in Group 1. A total of 31 ± 2 doses will be administered in three courses, the exact format for which will be presented in the Pharmacy Manual.

Group 1A participants will nominally receive 17 of their 31 ciprofloxacin doses in the clinic whereas Group 1B will nominally receive two of their 31 ciprofloxacin doses in the clinic. The

AV7909 Anthrax Vaccine

IND 014451

Protocol EBS.AVA.210, Version 3.0 (28 October 2019)

remaining doses will be taken at home. Doses should be taken at the same times \pm 30 min each day. Doses administered in the clinic will be recorded by the staff with the date and time of administration in each participant's source documents and eCRF. Doses self-administered at home will be recorded by the participant with time of administration in their e-diary. Refer to [Section 8.3.5.1](#) for additional details on the e-diary. If a participant misses a dose, they should be instructed to take the dose as soon as remembered, but no later than within 4 hours of its scheduled time. The participant should then wait until the next scheduled dose. The participant should not take two doses at the same time.

Exact details regarding the format in which the doses will be provided to the participants will be provided in the Pharmacy Manual.

Certain foods and over-the-counter products can interfere with the absorption of ciprofloxacin so prior to administration of doses in the clinic, site staff should ask each participant if they have eaten certain dairy products (such as milk or yogurt) or taken magnesium/aluminum antacids, other highly buffered drugs, or other products containing calcium, iron or zinc since their last dose and if so record this information along with the timing of intake, eg, 6 hours since their last dose. This information along with other precautions that need to be followed when taking ciprofloxacin will be provided to participants when they are given their supplies of ciprofloxacin for self-administration (see [Section 5.3.1](#)).

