8.1.3. Group 1B: Ciprofloxacin + AV7909 without Ciprofloxacin PK

Shown in [Table 6](#) is a schedule of events for Group 1B participants from screening until the end of the study. Following the table are detailed descriptions of the activities that the sites are expected to conduct for each of the column headings identified in the table once each participant has received his or her group assignment. Note that this detail starts following randomization for Group 1B which is when they receive their first course of ciprofloxacin although the actual activities for the trial do not begin until Day 4 when participants self-administer their first dose

AV7909 Anthrax Vaccine

IND 014451

Protocol EBS.AVA.210, Version 3.0 (28 October 2019)

of ciprofloxacin. The detailed activities during Screening and Group Assign (Randomization) were covered previously in [Section 8.1.1](#).

Table 6: Schedule of Events for Group 1B: Ciprofloxacin + AV7909 without Ciprofloxacin PK

	Screening	Group Assign	At Home†	Vac	At Home†	TNA	Final Visit	Safety Calls	EWV USV‡
Study Day(s)	-28 to -2	1	4-7	8 23*	9, 22, 24, 31-37	37	51	114, 205, 296, 388	NA
Visit Window	NA	NA		*± 1 d		± 1 d	± 1 d	± 14 d	
Sign, date ICF & assign ID	X								
Review eligibility ^a	X	X		X					
Medical history & demographics	X	X							
Physical examination ^b	X						X		X
ECG ^c	X								
Vital signs ^d	X	X		X			X		X
Pregnancy test ^e	X	X		X			X		X
FSH test ^e	X								
Collect sample for hematology ^f	X						X		X
Collect sample for serum chemistry ^g	X						X		X
Collect sample for urinalysis ^h	X						X		X
Urine drug screen ⁱ	X								
HIVAb/HBsAg/HCVAb	X								
Concomitant medications ^j	X	X		X		X	X	X	X
Randomize eligible participants		X							
Symptom-directed PE ^k		X		X					
Blood draws for TNA ^l		X				X			
Cipro dosing & compliance ^{m,n}		X	X	X	X	X			X ⁿ
AV7909 vaccination ^o				X					
Participant e-diary + tools ^p		X	X	X	X	X	X		X
Staff review of e-diaries ^q			X	X	X	X	X		X
AEs ^r , SAEs & AESIs ^s	X	X		X			X	X	X
Collect TSH & autoantibody samples ^t		X					X		X

For the abbreviations used above please refer to [Table 1](#) of the protocol. *The ± 1 d window applies only to the second vaccination on Day 23 (note: the second course of antibiotic treatment will have to shift accordingly). †At Home Days are only those days where both doses of ciprofloxacin are taken at home. ‡For EWV occurring within the visit window of Day 37, a blood sample for TNA will be drawn.

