^a Eligibility will be reviewed before each vaccination, ie, on Day 8 and Day 23.

^b Physical examinations (PE) will be conducted as described in [Protocol Section 8.3.3](#).

^c ECGs will be conducted and interpreted at screening as described in [Protocol Section 8.3.3](#).

^d Vital signs will be administered as described in [Protocol Section 8.3.4](#).

^e Pregnancy tests (serum and/or urine) will be administered to all WOCBP as described in [Protocol Section 8.3.2](#). Serum pregnancy test will be performed at Screening visit for WOCBP, while urine pregnancy tests for WOCBP will be required before each vaccination. At Screening visit only, FSH test will be performed for postmenopausal women.

^f Hematology will be conducted as described in [Protocol Section 8.3.2](#).

AV7909 Anthrax Vaccine

IND 014451

Protocol EBS.AVA.210, Version 3.0 (28 October 2019)

^g Serum chemistry will be conducted as described Protocol Section 8.3.2.

^h Urinalysis will be conducted as described in Protocol Section 8.3.2.

ⁱ Urine drug screens will be conducted as described in Protocol Section 8.3.2.

^j Concomitant medications will be identified and recorded as described in Protocol Section 6.5.

^k Symptom-directed PEs will be conducted as described in Protocol Section 8.3.3.

^l Blood samples for TNA assessment on Day 1 will be collected in the morning following randomization. Those on Day 37 will be collected after the final dose of ciprofloxacin has been administered. A TNA sample will also be collected if EWV occurs within the visit window of Day 37 as described in Protocol Section 8.1.8.

^m Participants receive their first course of ciprofloxacin following randomization. Format of the doses and distribution of subsequent courses will be described in the Pharmacy manual. Self-administration of ciprofloxacin starts on Day 4. Ciprofloxacin dose compliance will be managed as described in Protocol Section 6.4.

ⁿ Ciprofloxacin doses (500 mg po q 12 hr) will be administered as described in Protocol Section 6.1.2.

^o Vaccinations with AV7909 will be administered as described Protocol Section 6.1.4.

^p All participants will be provided with an e-diary for post vaccination follow up along with a thermometer and an injection site reaction measurement tool. Participants in Group 1 and 2 will be provided with an e-dairy for antibiotic compliance. All participants will be trained on the use of these tools and the e-diaries as described in Protocol Section 8.3.5.1.

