**Figure 1 Study Design for EBS.AVA.210**

[figure not shown]

cipro = ciprofloxacin; doxy = doxycycline; PK = pharmacokinetics; po = per os, (oral); q12 h = every 12 hours; TNA = toxin-neutralizing antibody; TSH = thyroid-stimulating hormone

aIn Group 1, the evening dose on Day 37 is not administered. bAntibiotic dosing for Groups 1 & 2 up to Day 8 is to enable 2 PK sessions prior to vaccination #1 (vac #1) on Day 8. Dosing continues on Day 9, extends around vac #2 (on Days 22 to 24) and then discontinues until Day 31 (cipro) or Day 32 (doxy). Cipro dosing continues from Day 31 to Day 37 and doxy dosing continues from Day 32 to Day 38, encompassing 2 PK sessions after the complete vaccination regimen as well as the blood draw for TNA. cSolid lines at Days 1, 8, 23, 37 and 51 are days when all groups have in-clinic visits. Days in red are those when Groups 1A and/or 2A have clinic visits for blood draws for pre-dose, trough values or PK.

All visits are performed on an outpatient basis, except Groups 1A and 2A participants will be admitted to the clinic in the evening for an overnight stay on days preceding serial (all day) blood collections needed for determination of cipro or doxy concentrations. For Group 1A, those samples will be taken on Days 4, 8, 31, and 35; for Group 2A, those samples will be taken on Day 2, 8, 32, and 38. AV7909 vac #1 will be administered to all groups on Day 8. For Groups 1B, 2B, and 3, it will be their first clinic visit after randomization and for Groups 1A and 2A, vaccination will occur in the evening following the second PK session. AV7909 vac #2 will be administered on Day 23. The final blood draw for TNA will be on Day 37 for all groups. There will be a final visit for safety for all groups on Day 51, four weeks after the last dose of AV7909, which is when the final blood draw for TSH & autoantibodies will also be collected.

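### The documents disagree on whether Group 1 takes one or two ciprofloxacin doses on Day 37, so the planned total is 31 or 32 depending on the passage read.

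*Protocol*

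**What the plan says.** Passages that imply two doses on Day 37:

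- Protocol 8.1.3.5 (Group 1B): "On Days 31 to 37, the participant is to self-administer ciprofloxacin 500 mg po every 12 hours at home". There is no evening exception, and the section's own heading stops at Day 36.
- Protocol Table 6 (Group 1B) includes Day 37 in an at-home column (9, 22, 24, 31-37). Table 5 (Group 1A) does the same (9, 22, 24, 36, 37). Both tables carry the footnote "At Home Days are only those days where both doses of ciprofloxacin are taken at home".

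Passages that imply one dose on Day 37:

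- Figure 1 footnote a, in protocol 4.1 and again in SAP 2.2.1: "In Group 1, the evening dose on Day 37 is not administered".
- Protocol 6.1.5: "A total of 31 ± 2 doses will be administered in three courses", and "Group 1A participants will nominally receive 17 of their 31 ciprofloxacin doses in the clinic". The same section puts two of Group 1B's 31 doses in the clinic. The Synopsis gives the self-administered shares as 14/31 and 29/31.
- Table 5 footnote n and Table 6 footnote l, on the TNA samples: "Those on Day 37 will be collected after the final dose of ciprofloxacin has been administered". Sections 8.1.2.14 and 8.1.3.6 have participants arrive at that visit with the morning dose already taken.

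The Synopsis schedule, "Group 1 on Days 4-9, Days 22-24 and Days 31-37", every 12 hours, fits either reading and does not settle the point.

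**The concern.** These are dosing instructions for healthy volunteers, so the number of doses should not turn on which page is consulted. Section 4.3.2 gives the aim of intermittent dosing as "restricting the antibiotics administered to the minimum to achieve these ends", which makes the exact count part of the design rationale.

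The Day 37 visit lists do not close the gap. In 8.1.2.14 and 8.1.3.6 staff count and record the remaining tablets, but neither list says that dosing is finished or that tablets are to be kept. Group 2A, by contrast, is told on Day 38 (8.1.4.13) that the supply is retained and which dose was the last. Section 6.4 has staff collect leftovers when a course is complete, and for Group 1 the end of the course is the point in dispute.

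There is also a small analysis question. SAP 5.4.1 and 8.6.3 need a required number of doses, and that number depends on the answer.

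**Working it through.** **Inputs.** Dosing days 4-9, 22-24 and 31-37, every 12 hours (Synopsis). Stated total 31 ± 2 (6.1.5). Clinic/home splits 17/14 for 1A and 2/29 for 1B (6.1.5 and Synopsis). Place of each dose from 8.1.2.1 to 8.1.2.14 (1A) and 8.1.3.1 to 8.1.3.6 (1B).

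**Total by course (two doses per day, except Day 37 as shown)**

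| | Days 4-9 | Days 22-24 | Days 31-37 | Total |
|---|---|---|---|---|
| One dose on Day 37 | 6 × 2 = 12 | 3 × 2 = 6 | 6 × 2 + 1 = 13 | 31 |
| Two doses on Day 37 | 12 | 6 | 7 × 2 = 14 | 32 |

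The stated 31 is reproduced exactly with one Day 37 dose and not with two.

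**Split, Group 1A**

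- Clinic: Day 4 (2), Day 5 (1), Day 6 (1), Day 7 (2), Day 8 (2), Day 23 (1), Day 31 (2), Day 32 (1), Day 33 (1), Day 34 (2), Day 35 (2) = 17.
- Home: Day 5 (1), Day 6 (1), Day 9 (2), Day 22 (2), Day 23 (1), Day 24 (2), Day 32 (1), Day 33 (1), Day 36 (2), Day 37 morning (1) = 14.
- With a Day 37 evening dose the split would be 17/15.

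**Split, Group 1B**

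- Clinic: Day 8 (1), Day 23 (1) = 2.
- Home: Days 4-7 (8), Day 8 evening (1), Day 9 (2), Day 22 (2), Day 23 evening (1), Day 24 (2), Days 31-36 (12), Day 37 morning (1) = 29.
- With a Day 37 evening dose the split would be 2/30.

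Both stated splits are reproduced only with one Day 37 dose.

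**What the ± 2 covers.** Sections 8.1.2.14 and 8.1.3.6 say the required number of doses varies if the Day 37 visit moves by a day. One day at two doses per day is 2 doses, so the range is 31 − 2 = 29 to 31 + 2 = 33. That matches the tolerance and leaves the unshifted count at 31.

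**Effect on the analyses**

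- Immunogenicity Population (at least 50% of specified doses): 0.5 × 31 = 15.5, so 16 doses; 0.5 × 32 = 16 doses. No change.
- PK Population: its in-clinic dose criterion ends on the morning of Day 35. No change.
- TNA and PK values: the last ciprofloxacin PK session is Day 35, and the TNA draw follows the Day 37 morning dose. A Day 37 evening dose comes after both.
- Dose compliance (SAP 5.4.1): 32/31 = 103% if 32 are taken against a required 31; 31/32 = 96.9% if 31 are taken against a required 32.
- E-diary compliance (SAP 8.6.3), top category above 75%, Group 1B: course three needs 10 of 13 entries (76.9%) or 11 of 14 (78.6%); overall it needs 22 of 29 (75.9%) or 23 of 30 (76.7%). The threshold moves by one entry in a descriptive table.

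**The case against.** The strongest reply is that this is a drafting slip which the rest of the documents resolve. Figure 1 footnote a speaks directly to the Day 37 evening dose. The totals and splits agree with it, and the visit text for that day, 8.1.3.6, refers only to a morning dose. No passage says in so many words that two doses are taken on Day 37. Participants are also guided by e-diary reminders and the Pharmacy Manual, not by protocol pages. Much of this stands, and it is why the point is small. It does not remove the conflict: 8.1.3.5 orders 12-hourly dosing through Day 37, the table footnote limits at-home days to those with both doses, and a footnote to a figure does not correct either. What the e-diary prompts and the Pharmacy Manual specify cannot be seen in these documents.

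A reader might infer four stronger things that the documents do not support.

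- That Groups 1A and 1B would be dosed differently. Section 8.1.3.5 covers 1B only, and for 1A the conflict rests on Table 5. The Day 37 visit text and the TNA footnotes are nearly the same for both subgroups.
- That compliance would exceed 100%. SAP 5.4.1 takes the required total from Figure 2, which is not shown, so a denominator of 31 cannot be confirmed. The 5.4.1 summaries count participants reaching 50% of doses or the in-clinic minimum, and neither count changes at 32 doses.
- That 32 doses breaks the protocol's total. It lies inside 31 ± 2. The argument rests on the nominal 31 and the two splits.
- That the evening dose is the mistake. That is a dosing decision, and this review does not make it.

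**Conclusion.** The contradiction is real and minor. Section 8.1.3.5 and the at-home columns of Tables 5 and 6 imply 32 doses. Figure 1 footnote a, the nominal total, both splits and the TNA footnotes imply 31. The size is one dose per participant, after the last PK and TNA samples. Sample size, power, alpha, the TNA and PK results, the 50% rule and the analysis populations are unchanged.

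This assumes that the Day 37 visit is not shifted, that the TNA draw takes place before the evening dose would fall due, and that the home and clinic doses follow the section 8.1 visit text. How many participants would actually take 31 or 32 doses cannot be estimated from these documents.

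**What to change.** The sponsor should state the last ciprofloxacin dose once, for Groups 1A and 1B together, and bring these places into line with it: the heading and text of 8.1.3.5, the at-home columns of Tables 5 and 6 (or the footnote defining them), Figure 1 footnote a in both documents, the dose total in 6.1.5, and TNA footnotes n and l. It should also confirm that the required dose count in Figure 2, which SAP 5.4.1 and 8.6.3 use, is the same number. The cost is text edits to a few lines, a check of Figure 2 and a memo to sites. No design or analysis change follows.

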8.1.3.6. Group 1B: Day 37 (\pm 1 d) – Blood Draw for TNA

The Day 37 Visit may shift by \pm 1 d. If such a shift occurs, the participant must remain on ciprofloxacin 500 mg po every 12 hours until the morning before the blood draw. In the event of such a shift, the participant's required number of doses of ciprofloxacin will vary. The Pharmacy Manual will contain a table detailing the dosing options for the final course of ciprofloxacin given a one-day shift from Day 37.

1. Participants will report to the clinic having taken their morning dose of ciprofloxacin at home.
2. Review participant's ciprofloxacin supply; count the number of remaining doses and compare to the e-diary record to document compliance; record total remaining in source document.

AV7909 Anthrax Vaccine

IND 014451

Protocol EBS.AVA.210, Version 3.0 (28 October 2019)

3. Review other e-diary entries with participant. Discuss any changes in the use of concomitant medication as well as any vaccination reactions if still ongoing. Remind participants that they should still use sunscreens and avoid excessive sun exposure and strenuous sports until the Day 51 Final Study Visit.
4. Record concomitant medications.
5. Collect blood sample for TNA assessment

8.1.3.7. Group 1B: Day 51 (± 1 d) – Final In-Clinic Study Visit

1. Perform complete PE.
2. Review e-diary entries with participant and collect hand-held device if study provided.
3. Review and record AEs.
4. Record concomitant medications.
5. Assess vital signs (seated/semi-recumbent blood pressure, heart rate, respiratory rate and temperature).
6. For WOCBP, collect and perform UPT. Positive UPTs will be confirmed with a serum pregnancy test. All confirmed pregnancies in participants who receive at least one dose of AV7909 or ciprofloxacin and where conception occurs prior to 12 months after last receipt of either IP will be followed to outcome.
7. Collect blood sample for hematology.
8. Collect blood sample for serum chemistry.
9. Collect blood sample for TSH and aut antibodies.
10. Collect urine sample for urinalysis.

8.1.4. Group 2A: Doxycycline + AV7909 with Doxycycline PK Sessions

Shown in [Table 7](#) is a schedule of events for Group 2A participants from screening until the end of the study. Following the table are detailed descriptions of the activities that the sites are expected to conduct for each of the column headings identified in the Table. Note that this detail starts with PM Admit (Evening Admission) as the detailed activities during Screening and Group Assign (Randomization) were covered previously in [Section 8.1.1](#).

Table 7: Schedule of Events for Group 2A: Doxycycline + AV7909 with Doxycycline PK

	Screening	Group Assign	PM ^a Admit	PK ^b	AM ^a Visits	Vac	At Home [†]	TNA	Final Visit	Safety Calls	EWV USV [‡]
Study Day(s)	-28 to -2	1	1 ^r , 7 ^{c,e} , 31, 37	2 ^r , 8, 32, 38	3-7, 33-37	8, 23 ^{e,*}	9, 22, 24,	37	51	114, 205, 296, 388	NA
Visit Window ±	NA		§+ 1 d	NA		*± 1 d			± 1 d	± 14 d	
Read, sign, date ICF & receive ID	X										
Review eligibility	X	X	X			X ^c					

AV7909 Anthrax Vaccine

IND 014451

Protocol EBS.AVA.210, Version 3.0 (28 October 2019)

	Screening	Group Assign	PM ^a Admit	PK ^b	AM ^a Visits	Vac	At Home [†]	TNA	Final Visit	Safety Calls	EWV USV [‡]
Study Day(s)	-28 to -2	1	1 ^r , 7 ^{c,e} , 31, 37	2 ^r , 8, 32, 38	3-7 33-37	8 23 ^{e*}	9, 22, 24,	37	51	114, 205, 296, 388	NA
Visit Window \pm	NA		\pm 1 d	NA		\pm 1 d			\pm 1 d	\pm 14 d	
Medical history & demographics	X	X									
Physical examination ^d	X								X		X
ECG ^e	X										
Vital signs ^f	X	X		X		X			X		X
Pregnancy test ^g	X	X	X (D7 only)			X			X		X
FSH test ^g	X										
Collect sample for hematology ^h	X								X		X
Collect sample for serum chemistry ⁱ	X								X		X
Collect sample for urinalysis ^j	X								X		X
Urine drug screen ^k	X										
HIVAb/HBsAg/HCVAb	X										
Concomitant medications ^l	X	X	X	X	X	X	X	X	X	X	X
Randomize eligible participants		X									
Symptom-directed PE ^m		X				X			X		
Blood draws for TNA ⁿ		X						X			
Doxy dosing & compliance ^{o,p}			X	X	X	X	X	X			X
Doxy pre-dose or trough				X	X						
Doxy PK ^q				X							
AV7909 vaccination ^r						X					
Participant e-diary + tools ^x		X		X	X	X	X	X	X		X
Staff review of e-diaries ^t			X	X	X	X	X	X	X		X
AEs ^u , SAEs, AESIs ^v	X	X	X	X		X			X	X	X
Collect TSH & autoantibody samples ^w		X							X		X

For the abbreviations used above please refer to [Table 1](#) of the protocol. *The \pm 1 d window applies only to the second vaccination on Day 23 (note: the second course of antibiotic treatment will have to shift accordingly). [†]At Home Days are only those days where both doses of doxycycline are taken at home. [§]The +1 d window only applies to Day 31. [‡]For EWV occurring within the visit window of Day 37, a blood sample for TNA will be drawn.

^a PM and AM admissions must be timed so that doxycycline can be administered in the clinic within a 12 hr \pm 30 min window of the prior AM or PM dose.

^b For each PK session, the sites will manage the meals and activity of participants as detailed in [Protocol Section 5.3.1](#) and [Protocol Section 5.3.2](#).

^c Eligibility will be reviewed before each vaccination, either the evening before (ie, on Day 7) or the morning of vaccination (ie, on Day 23).

^d Physical examinations (PE) will be conducted as described in [Protocol Section 8.3.3](#).

^e ECGs will be conducted and interpreted at screening as described in [Protocol Section 8.3.3](#).

^f Vital signs will be administered as described in [Protocol Section 8.3.4](#).

^g Pregnancy tests (serum and/or urine) will be administered to all WOCBP as described in [Protocol Section 8.3.2](#). Serum pregnancy test will be performed at Screening visit for WOCBP, while urine pregnancy tests for WOCBP required before each vaccination will be performed either the evening before (ie, on Day 7) or the morning of vaccination (ie, on Day 23). Note: for WOCBP in group 2A, UPT is required only at Day 7 (at the evening admission); it is not required at evening admissions at Day 1, 31 or 37. FSH test will be performed at Screening visit only for postmenopausal women.

AV7909 Anthrax Vaccine

IND 014451

Protocol EBS.AVA.210, Version 3.0 (28 October 2019)

^h Hematology tests will be conducted as described in Protocol Section 8.3.2.ⁱ Serum chemistry tests will be conducted as described Protocol Section 8.3.2.^j Urinalysis will be conducted as described in Protocol Section 8.3.2.^k Urine drug screens will be conducted as described in Protocol Section 8.3.2.^l Concomitant medications will be identified and recorded as described in Protocol Section 6.5.^m Symptom-directed PEs will be conducted as described in Protocol Section 8.3.3.ⁿ Blood samples for TNA assessment on Day 1 will be collected in the morning following randomization. Those on Day 37 will be collected after the morning dose of doxycycline has been administered. A TNA sample will also be collected if the EWV occurs within the visit window of Day 37 as described in Protocol Section 8.1.8.^o Symptom-directed PEs will be conducted as described in Protocol Section 8.3.3.^p Doxycycline dose compliance will be managed as described in Protocol Section 6.4.^q Doxycycline doses (100 mg po q 12 hr) will be administered as described in Protocol Section 6.1.6.^r Blood samples for assessment of doxycycline concentrations will be collected as detailed in Protocol Section 8.4.^t Vaccinations with AV7909 will be administered as described Protocol Section 6.1.4.^s All participants will be provided with an e-diary for post vaccination follow up along with a thermometer and an injection site reaction measurement tool. Participants in Group 1 and 2 will be provided with an e-dairy for antibiotic compliance. All participants will be trained on the use of these tools and the e-diaries as described in Protocol Section 8.3.5.1.^l Staff will begin reviewing the e-diaries on Day 3 and will review them at routine intervals thereafter.^u AEs will be collected at all clinic visits through Day 51/EWV as described in detail in Protocol Section 9.^v AEs, SAEs and potential AESIs will be collected during the Safety Follow-Up Telephone Calls (see Protocol Section 8.1.7).^w Serum samples for TSH & autoantibody testing will be collected from all participants and tested as described in Protocol Section 8.3.2 (ie, at Day 1, Day 51, and at EWV if the subject received at least one vaccination). Additional TSH & autoantibody testing may be requested (ie, based on the participant's report(s) of a potential AESI); additional TSH and/or autoantibody testing should be performed as part of an unscheduled visit.**8.1.4.1. Group 2A: Day 1 – Overnight Stay # 1**

1. Admit to the clinic for overnight stay #1.
2. Review eligibility.
3. Review and record AE assessments and changes in concomitant medications in participant's medical history unless they are related to study procedures in which case they are recorded as AEs.

